6 MEDICAL HISTORY.....	12
7 PRIOR AND CONCOMITANT MEDICATIONS.....	13
8 STUDY PROCEDURES AND SCHEDULE	13
8.1 Overview of safety data	13
8.2 Description of study steps.....	14
8.2.1 Completion of the on-line questionnaire by the HCP	14
8.2.1.1 Website access and registration	14
8.2.1.2 Enrolment Steps.....	14
8.2.1.3 Completion of the Pregnancy Outcome Forms	15
8.2.1.4 Completion of the 4-month Follow-Up HCP Forms	15
8.2.2 Completion of the on-line questionnaire directly by the woman:.....	15
8.2.2.1 Website access and enrolment	16
8.2.2.2 Completion of the Pregnancy and Outcome Forms	16
8.2.2.3 Completion of the 4-month Follow-Up Woman Form	16
8.3 Participant follow-up	17
8.4 Methods of data collection.....	17
9 STATISTICAL PROCEDURES	18
9.1 Sample size justification	18
9.2 Statistical analyses	19
9.2.1 Study Population	19
9.2.2 Statistical analysis	19
9.2.2.1 Descriptive analysis	19
9.2.2.2 Primary Objective Assessments	20
9.2.2.3 Secondary Objective Assessments	21

9.2.2.4	Statistical testing and multi-variable analysis	21
10	SPONSOR PHARMACOVIGILANCE RESPONSIBILITIES	22
11	DATA MONITORING BOARD	22
11.1	Assessment of pregnancy outcome	22
11.2	DMB assessment	22
11.3	DMB working procedures.....	23
12	ETHICAL AND LEGAL ASPECTS	23
12.1	Women information and informed consent.....	23
12.2	Confidentiality and data protection	23
12.3	Observational study approval.....	24
12.4	Ongoing information for IRB	24
13	MONITORING	24
14	DOCUMENTATION AND USE OF STUDY FINDINGS.....	24
14.1	Documentation of study findings.....	24
14.2	Use of study findings.....	25
15	STUDY DURATION AND DATES	25
ANNEX 1: REFERENCES AND STATISTICAL TABLES		26
ANNEX 2: PARTICIPANT CONSENT FORM AND HIPAA AUTHORIZATION AGREEMENT		28
PARTICIPANT CONSENT FORM.....		30
HIPAA AUTHORIZATION AGREEMENT		32

PROTOCOL SYNOPSIS

Title

Prospective, Observational Study to Assess Clinical Follow-up and Outcomes of Pregnancies Exposed to ella® (ellipse II).

Phase

IV

Indication

Emergency contraception within 120 hours (5 days) of unprotected sexual intercourse or contraceptive failure (Marketing Authorization NDA 022474 dated 13 August 2010).

Objectives*Primary objective:*

To assess the rates of occurrence of outcomes of pregnancies exposed to ella® (whether due to failure of the emergency contraception or inadvertent exposure during pregnancy). Data analysed will come from this prospective observational study, other studies and pharmacovigilance reporting.

Secondary objectives:

To collect data on fetal and neonatal outcomes, birth and maternal complications in case of pregnancies exposed to ella®.

To assess the nature and incidence of complications of pregnancy loss in pregnancies exposed to ella®.

Design

Prospective observational study.

Population

Pregnant women in the USA, who have been exposed to ella®:

- during the menstrual cycle in which the pregnancy started or
- at any time during pregnancy.

Women will be directly enrolled in the study using a website interface that will be accessible to Health Care Professionals (HCP) and women themselves.

Sample size

A sample size of 400 pregnancies with known outcome was chosen as it provides 80% power to detect a two-fold increase (Risk Ratio=2) for events with a proportion of 3% and a three-fold increase (RR=3) for events with a proportion of 1% (e.g., approximately equivalent to the total prevalence of congenital heart defects).

Data collection

Detailed clinical data on ella® exposure, pregnancy course and pregnancy outcomes, including fetal and neonatal outcomes, maternal pregnancy complications, medical history and use of other medications will be collected online using the study website.

Statistical analyses

The data collected in this study will be pooled with all reports of pregnancies collected by the Sponsor which include outcome information. Additional data sources include other clinical trials and Pharmacovigilance reporting. Pregnancy outcomes will be analyzed on the pooled dataset.

Baseline characteristics data of enrolled and completed cases will be described: age, pregnancy status at time of ella® exposure, dates of unprotected intercourse, last menstrual period, and ella® intake.

Each pregnancy outcome will be described as a proportion of pregnancies, with 95% exact confidence intervals.

Birth, maternal and pregnancy complications will be evaluated for each individual case, and the relationship with ella® exposure will be assessed according to the standard Pharmacovigilance process.

Proportions of adverse outcomes of ella®-exposed pregnancies will be compared with those from a suitable general reference population that would comprise essentially all non-exposed pregnancies, e.g. for congenital anomalies, population would be based on data from registries for congenital anomalies, notably members of the European Surveillance of Congenital Anomalies, EUROCAT.

Sponsor's pharmacovigilance responsibilities

All cases will be managed according to the sponsor's Pharmacovigilance processes, in line with the applicable legislation.

Whenever applicable, individual case safety reports (ICSRs) will be submitted to Health Authorities on an expedited basis according to current regulations.

Progress status updates will be given in each Periodic Safety Update Report (PSUR) and Development Safety Update Report (DSUR) if applicable.

Additionally, a descriptive analysis of the data collected will be provided annually in the PSUR.

Study duration and dates

Recruitment of women will be done using a website access. Implementation of the website is planned for the second quarter of 2014 and website will be in place during the whole course of the study.

STUDY SCHEDULE

Period of pregnancy Study procedures	Enrolment in the study	Pregnancy Course	End of pregnancy	4 months FU ³
Written ¹ informed consent	X			
Inclusion criteria	X			
Pregnancy diagnosis	X			
ella [®] exposure	X			
Prior and concomitant medications	X	X	X	
Recreational drug use (tobacco, alcohol, illicit drugs)	X	X	X	
Serology and prenatal tests results	X			
Medical history	X			
Maternal and fetal pregnancy complication	X	X	X	
Pregnancy outcome ²			X	
Live birth follow-up ³				X

¹: Signed ICF will be collected according to local regulations. When completed by the HCP, prior starting the questionnaire completion, the ICF will be downloaded from the website and a print-out copy signed by the woman. When completed by the woman, prior starting the questionnaire completion, an electronic signature will be requested on the ICF module and the woman will be requested to save and/or print the ICF for her records.

²: Possible pregnancy outcomes are: Live birth (healthy baby, congenital anomaly or other neonatal diagnosis, or neonatal death); pregnancy loss (spontaneous abortion or ectopic pregnancy or induced abortion, premature stillbirth)

³: In case of live birth, the period of observation of the study will last for 4 months post-delivery to access possible congenital anomalies that may not be detected at birth.

ABBREVIATIONS AND DEFINITIONS

ADR	Adverse Drug Reaction
AE	Adverse Event
AFP	Alpha-Fetoprotein
CFR	Code of Federal Regulations
CHMP	Committee for Medicinal Products for Human Use
CRO	Contract Research Organization
DMB	Data Monitoring Board
DSUR	Development Safety Update Report
EC	Emergency Contraception
EUROCAT	European Surveillance of Congenital Anomalies
ICBDSR	International Clearinghouse for Birth Defects Surveillance and Research
ICF	Informed Consent Form
ICSR	Individual Case Safety Report
EMA	European Medicines Agency
FDA	Food and Drug Administration
HIPAA	Health Insurance Portability and Accountability Act
ICF	Informed Consent Form
IRB	Institutional Review Board
LMP	Last Menstrual Period
NDA	New Drug Authorization
PI	Prescribing Information
PL	Patient Leaflet
PSUR	Periodic Safety Update Report
RR	Risk Ratio
SAE	Serious Adverse Event
TOPFA	Terminations Of Pregnancy for Fetal Anomaly
UPA	Ulipristal Acetate
USA	United States of America

1 INTRODUCTION AND STUDY RATIONALE

ella[®] (ulipristal acetate 30 mg tablet) is a selective progesterone modulator with antagonistic and partial agonist effects at the progesterone receptor. Ulipristal acetate [17alpha-acetoxy-11beta-(4-N,N-dimethylaminophenyl)-19-norpregna-4,9-diene-3,20 dione] was initially developed at the US National Institutes of Health. HRA Pharma acquired the license rights of the compound in 2000 and has been developing it ever since. The compound has been tested in an extensive battery of non-clinical and clinical studies and was approved for marketing New Drug Authorization (NDA) at the dose of 30 mg (tablet) for emergency contraception up to 120 hours (5 days) in the European Union (EU/1/09/522/001) and the United States of America (NDA 022474), in May 2009 and August 2010 respectively.

During the clinical development phase, only a small number of pregnancies have occurred following administration of ella[®]. During the evaluation process of the ella[®] registration dossier, the EMA (European Medicines Agency) and FDA (Food and Drug Administration) requested additional information on the potential effects of ella[®] exposure on pregnancy course and outcome.

HRA Pharma committed to collecting information on clinical follow-up and outcomes of pregnancies that begin following ella[®] failure as well as pregnancies inadvertently exposed to ella[®] by putting in place:

- A voluntary web-based pregnancy registry available in all European countries where the product is launched and accessible to all ella[®] prescribers;
- An observational study, targeting 1000 investigators in the Europe and the USA (ellipse).

After several months of efforts to conduct the observational study required in PMR 1673-1 (ellipse), HRA Pharma came to the conclusion that it was highly unlikely that it would ever be able to recruit the target site prescribers and that, also due to the very low rate of ella[®] failure, the number of reported pregnancies would remain extremely limited.

Indeed, the process of selection of investigators began in May 2011 in the European Union. At that time, over 6,000 healthcare providers (HCPs) were contacted. Due to a disappointing response rate, an additional 3,700 providers were contacted started in September 2011. The first site was initiated in June 2011 and 219 sites had been initiated in Europe by end 2012. Eight pregnant women have been identified, and actions have been undertaken to increase the number of selected sites in Europe. In the US, finding investigational sites has found to be even more difficult since the use of ella[®] is very low and limited to family planning clinics which typically do not follow-up women after they become pregnant. Several institutions providing emergency contraception were contacted from December 2010. In September 2011, in order to reach a larger number of HCPs in the USA, an information document was prepared for distribution during 10 medical congresses held in October and November throughout the territory. About 2,600 attendees were expected to participate in these congresses. No feedback from HCPs has ever been received. At this time, no US site has been able to or interested in participating in the study.

There was therefore a clear need to change the way pregnancy data are obtained in order to collect information on pregnancy outcomes after ella[®] exposure.

Following consultation with European authorities (EMA), it was decided to redirect efforts from the observational study towards improving the existing online pregnancy registry. The EMA agreed that no additional sites would be initiated in the observational study and that data collection would be stopped once the improved web-based pregnancy registry was launched. The ellipse study progress was also discussed with the FDA during a Type C meeting held on November 15, 2012 and it was decided to amend the ellipse protocol to include the web-based enrollment and data collection.

2 STUDY OBJECTIVES

2.1 Primary objective

[figure not shown]
The primary objective of this observational study is to assess the rates of occurrence of outcomes of pregnancies exposed to ella® (whether due to failure of the emergency contraception or inadvertent exposure during pregnancy). Data analyzed will come from this prospective observational study, other studies and pharmacovigilance reporting.

2.2 Secondary objectives

The secondary objectives of this observational study are:

- To collect data on fetal and neonatal outcomes, birth and maternal complications in pregnancies exposed to ella®;
 - To assess the nature and incidence of complications of pregnancy loss in pregnancies exposed to ella®.

3 STUDY DESIGN AND SCHEMATIC REPRESENTATION OF THE OUTCOMES

* Women who do not want to provide her HCP contact details, will have the option to contact a referent physician who will be commissioned to follow-up directly with the woman.

** Questionnaire may be completed on-line either by the woman or the HCP at any time from pregnancy diagnosis up to known pregnancy outcome. For live birth (except for neonatal death), woman or the HCP will be requested to complete a follow-up questionnaire 4 months after the delivery date.

4 SELECTION OF WOMEN

4.1 Number of women

As per rationale detailed in section 9.1, a total of 400 ella®-exposed pregnancies with known outcomes will be analysed.

4.2 Enrolment process

Enrolling an exposed woman in the study will involve completing an online questionnaire either by the HCP or directly by the woman (see also section 8.1 Description of Study Steps).

4.2.1 Completion of HCP on-line questionnaires by the HCP

There will be a specific on-line questionnaire to be completed by the HCP where data on pregnancy diagnosis and exposure to ella® will first be collected. Once the pregnancy outcome is known, the HCP will be requested to complete the rest of the questionnaire.

For live birth, HCP will be requested to complete follow-up forms 4 months after the delivery date (**4-month Follow-Up HCP Form**).

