8.2.1.4 Completion of the 4-month Follow-Up HCP Forms

In case of live birth and 4 months after the delivery, the HCP be reminded to re-access the website. The HCP will be asked to:

- Access the website with the HCP unique user ID and password
- Collect the age, height and weight of the baby
- Collect congenital anomaly detected since birth, if applicable
- Collect late development detected since birth, if applicable
- Collect death data, if applicable.

8.2.2 Completion of the on-line questionnaire directly by the woman:

Up to three questionnaires will be completed by the woman: the first two ones including Pregnancy and Outcome Forms, and one for live birth only, a 4-month Follow-up Form.

* In case a woman completed the questionnaire on her own, she should be reminded to bring her unique patient number to allow the HCP to provide further information on the pregnancy if requested.

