8.2.2.3 Completion of the 4-month Follow-Up Woman Form

In case of live birth and four months after the delivery, the woman will receive an e-mail asking to re-access the website.

- Access the website and re-enter the unique file number provided by e-mail at the time of the Pregnancy and Outcome Forms submission

* Ideally the HCP in charge of the pregnancy follow-up (for e.g. midwife, obstetrician,...)

- Provide the age, height and weight of the baby
- Provide any congenital anomaly detected since birth, if applicable
- Collect late development detected since birth, if applicable

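### On the HCP route the 4-month infant form goes to the mother's enrolling HCP and cannot show whether the infant was assessed, so unassessed infants can count as free of late anomalies

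*Protocol*

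**What the plan says.** The footnotes to the Study Schedule give the purpose of the 4-month observation: to find congenital anomalies that delivery may not reveal.

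On the HCP route, Section 4.2.1 states: "For live birth, HCP will be requested to complete follow-up forms 4 months after the delivery date". Section 8.2.1.4 adds: "In case of live birth and 4 months after the delivery, the HCP be reminded to re-access the website". The first step there is "Access the website with the HCP unique user ID and password", and Section 8.2.1.1 issues those credentials when the HCP registers, before enrolling a woman. The person reporting on the infant is therefore the HCP who enrolled the mother.

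The content of the form is listed in Section 8.2.1.4. One item is unconditional: "Collect the age, height and weight of the baby". The next is conditional: "Collect congenital anomaly detected since birth, if applicable". Late development and death are conditional in the same way.

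On contacts, Section 8.2.1.2 asks for the clinician or midwife following the pregnancy, where there is one. Section 8.3 directs follow-up queries to the reporters, chiefly the HCP. Section 14.1, item 5, names the HCP or referent physician, or the woman where that applies, for the 4-month safety contact. No section asks for the infant's clinician.

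Section 9.2.2.2 divides live births with an anomaly by all live births, and classes a live birth without any anomaly as a healthy baby.

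**The concern.** The 4-month form is the study's only scheduled means of finding anomalies that emerge after delivery. Its value depends on the reporter knowing the infant. On the HCP route the protocol ensures that the reporter knew the mother while she was pregnant, and no more.

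If that HCP has no later knowledge of the infant, the anomaly item will be empty. From the listed items, that entry looks the same as one from an HCP who examined the infant and found nothing. Both infants then enter the denominator and both count as healthy.

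This differs from ordinary loss to follow-up. Section 9.2.2.1 promises to describe the proportion lost, but a returned form with an uninformed blank would not be seen as a loss.

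The error runs one way. Late anomalies can be missed among exposed infants but not invented, so observed prevalence falls relative to a registry that captures late-found cases. Section 9.2.2.2 states the aim as detecting a possible signal, and this bias works against detection.

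**Working it through.** **1. What the text fixes.** Taking the HCP-route steps in order:

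- Reporter at 4 months: the registered HCP, under that HCP's own login (4.2.1, 8.2.1.1, 8.2.1.4).
- Requirement that the reporter has examined the infant or seen a record: none stated.
- Alternative source: the pregnancy clinician's contact, if there is one (8.2.1.2). No infant clinician. The woman may be contacted where applicable (14.1, item 5), but no HCP-route step gives her the form.
- Way to tell 'none found' from 'not assessed': none among the listed items (8.2.1.4).
- External check: no routine on-site monitoring (Section 13).
- Use in analysis: all live births in the denominator (9.2.2.2).

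So the plan, followed as written, can count an unassessed infant as free of late anomalies. This conclusion needs no arithmetic.

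**2. The plan's own figures.** Annex 1, Table 1 gives 398 exposed pregnancies for 3% against 6%, and 392 for 1% against 3% (two-sided alpha 0.05, 1:10, 80% power). The two-proportion formula with continuity correction returns 398 and 392; without it, 362 and 339. The sample size arithmetic is not in question.

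**3. Illustration of size.**

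Inputs from the protocol: n1 = 400, n0 = 4,000 (1:10), two-sided alpha 0.05, reference live-birth prevalence p0 = 176 per 10,000 = 0.0176 (Table 2).

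Assumptions, not in the protocol: true risk ratio 2; a reference that includes late-found cases; all 400 are live births on the HCP route; a share m of all anomalies comes to light after birth and is unknown to the reporter.

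Observed exposed prevalence: p1 = 0.0352 × (1 − m). Observed risk ratio: 2 × (1 − m).

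Power = Φ{[(p1 − p0) − 1.96·s0] / s1}, where s0 = √[p̄(1 − p̄)(1/400 + 1/4,000)], s1 = √[p1(1 − p1)/400 + p0(1 − p0)/4,000] and p̄ = (400·p1 + 4,000·p0)/4,400.

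For m = 0: p̄ = 0.0192, s0 = 0.00720, s1 = 0.00945. The argument is (0.0176 − 0.01410)/0.00945 = 0.370, and power is 0.644.

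| m | p1 | observed RR | power | power with Table 1's continuity correction |
|---|---|---|---|---|
| 0 | 0.0352 | 2.0 | 64% | 59% |
| 0.1 | 0.0317 | 1.8 | 50% | 44% |
| 0.2 | 0.0282 | 1.6 | 35% | 29% |
| 0.3 | 0.0246 | 1.4 | 20% | 16% |

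**4. Dependence on the share of births on this route.** If a share w of live births is on the HCP route and capture is complete elsewhere, p1 = 0.0352 × (1 − m·w). With m = 0.2 and w = 0.25, p1 = 0.0352 × 0.95 = 0.0334, the observed risk ratio is 1.9 and power is about 58% (uncorrected), against 64% with full capture and 35% when w = 1.

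**The case against.** The strongest reply is that the text does not show enrolling HCPs to be ignorant of the infant. A reader might infer that they are, from the Introduction's remark that US use is "limited to family planning clinics which typically do not follow-up women after they become pregnant" and from the footnote "Ideally the HCP in charge of the pregnancy follow-up (for e.g. midwife, obstetrician". Neither supports that inference. The Introduction explains why US sites could not be found for the preceding study; Section 4.2.3 opens this one to HCPs generally. The footnote belongs to the woman-completed route, where she names her HCP. An enrolling obstetrician or family doctor may well know the child.

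A reader might also infer that a blank form is deemed completed follow-up, or that nobody examined the infant. No section says the first. On the second, a clinician the study never contacts may have done so. What stands is narrower: nobody reporting to the study need have looked.

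Three further points have weight:

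- Age, height and weight are requested unconditionally, so blanks there would give some warning. They are a partial check: a weight relayed by the family is not an assessment for anomalies.
- The form is not shown and may offer an 'unknown' answer. The protocol's item list does not.
- The sponsor may query reporters, visit in person, or contact the woman where applicable (8.3, 13, 14.1). These steps are discretionary or loosely worded, and none records whether the infant was assessed.

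Finally, the illustration is an upper case. The 400 are pregnancies with known outcome, including losses and induced abortions, and Section 9.2.1 pools them with trial and spontaneous reports. That limits the size, not the direction.

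**Conclusion.** The point holds as a gap in what the protocol collects. On the HCP route it neither secures a reporter who knows the infant nor records whether the infant was assessed, and it counts live births without an anomaly as healthy. Any late anomaly unknown to the enrolling HCP is then treated as absent, biasing live-birth and total prevalence downward.

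The size cannot be derived from the documents, which give neither the late-found share nor the split between routes. The fall from about 64% to between 50% and 20% power rests on 400 live births, all on this route, 10% to 30% of anomalies missed, a true risk ratio of 2 and a reference with complete late capture. A smaller share on this route gives a smaller loss.

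It should be corrected in the protocol, because no analysis can recover an item that was never asked.

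**What to change.** 1. In Sections 8.2.1.4 and 8.2.2.3, add to both 4-month forms: 'infant examined or infant record seen since birth: yes/no', with date and source. Replace the conditional anomaly item with yes/no/unknown. The woman's form needs this too, since it has the same conditional wording; sending the form to the mother would not by itself cure the ambiguity.
2. Treat 'no' or 'unknown' as 4-month follow-up not done. Report 4-month anomaly prevalence also among infants with a documented assessment, beside the all-live-births figure in Section 9.2.2.2.
3. In Sections 8.2.1.2 and 8.2.1.3, collect with consent either the infant clinician's contact or a sponsor-blinded e-mail address for the mother, for use when the enrolling HCP answers 'no'. The HCP-route list does not at present include the mother's e-mail; only the woman's route does (8.2.2.2).

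The cost is a few form fields, added consent and authorisation wording, and possibly a lower stated number of infants with completed 4-month follow-up.
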